#### CTCAE v4.0 general severity guidelines:

Grade	Severity	Description
1	Mild	Mild; asymptomatic or mild symptoms; clinical or diagnostic observations only; intervention not indicated.
2	Moderate	Moderate; minimal, local or noninvasive intervention indicated; limiting age-appropriate instrumental activities of daily living (ADL)*.
3	Severe	Severe or medically significant but not immediately life-threatening; hospitalization or prolongation of hospitalization indicated; disabling; limiting self-care ADL**.
4	Life-threatening	Life-threatening consequences; urgent intervention indicated.
5	Fatal	Death related to AE.

## **ADL**

\*Instrumental ADL refers to preparing meals, shopping for groceries or clothes, using the telephone, managing money, *etc.*

\*\*Self-care ADL refers to bathing, dressing and undressing, feeding self, using the toilet, taking medications, and not bedridden.

### 11.1.4 Assessment of relationship of AE to treatment

The possibility that the AE is related to study agent will be classified as one of the following: not related, unlikely, possible, probable, definite.

### 11.1.5 Follow-up of AEs

All AEs, including lab abnormalities that in the opinion of the investigator are clinically significant, will be followed according to good medical practices and documented as such.

## **11.2 Serious Adverse Events**

11.2.1 DEFINITION: Regulations at 21 CFR §312.32 (revised April 1, 2014) defines an SAE as any untoward medical occurrence that at any dose has one or more of the following outcomes:

- Death
- A life-threatening AE
- Inpatient hospitalization or prolongation of existing hospitalization
- A persistent or significant incapacity or substantial disruption of the ability to perform normal life functions
- A congenital anomaly or birth defect
- Important medical events that may not be immediately life threatening or result in death or hospitalization should also be considered serious when, based upon appropriate medical judgment, they may jeopardize the participant and may require intervention to prevent one of the other outcomes.

### 11.2.2 Reporting SAEs to DCP

11.2.2.1 The Lead Organization and all Participating Organizations will report SAEs on the DCP SAE Report Form found at <http://prevention.cancer.gov/clinical-trials/clinical-trials-management/protocol-information-office/pio-instructions-and-tools/2012-consortia>.

11.2.2.2 Contact the DCP Medical Monitor by phone or email within 24 hours of knowledge of the event.

[name]  
Chief, Lung & Upper Aerodigestive Cancer Research Group  
NCI/Division of Cancer Prevention  
[name]  
[name] (For FedEx, use [name])  
[contact]  
[contact]  
email: [[contact]](mailto:[contact])

Include the following information when calling the Medical Monitor:

- Date and time of the SAE
- Date and time of the SAE report
- Name of reporter
- Call back phone number
- Affiliation/Institution conducting the study
- DCP protocol number
- Title of protocol
- Description of the SAE, including attribution to drug

11.2.2.3 The Lead Organization and all Participating Organizations will email written SAE reports to the medical monitor and to DCP's Regulatory Contractor CCS Associates, Inc. (CCSA; [contact]) at [[contact]](mailto:[contact]) within 48 hours of learning of the event using the fillable PDF SAE Report Form.

11.2.2.4 The DCP Medical Monitor and CCSA regulatory and safety staff will determine which SAEs require FDA submission as IND safety reports.

11.2.2.5 The Lead Organization and all Participating Organizations will comply with applicable regulatory requirements related to reporting SAEs to the IRB/IEC.

### 11.2.3 Follow-up of SAE

Site staff should send follow-up reports as requested when additional information is available. Additional information should be entered on the DCP SAE Report Form in the appropriate format. Follow-up information should be sent to DCP as soon as available. An SAE will be followed until resolution. The follow-up plan will be documented in the participant's study records.

## 12. STUDY MONITORING

### 12.1 Data Management

All of the procedures outlined in the University of Wisconsin Chemoprevention Consortium standardized Data Management Plan (version dated 05/25/2018) will be followed in this protocol. Please refer to this document for additional details on data management procedures. The University of Wisconsin Carbone Cancer Center's OnCore database will be the database of record for the protocol and subject to NCI and FDA audit. OnCore is a web-based clinical trials database. Data entry will be performed by the CLO where staff is trained in OnCore and applicable regulatory requirements such as 21 CFR; Part 11. Data from the OnCore database will be transferred to Federal Security Compliant formats for transmission to DCP according to pre-established DCP standards and procedures.

### 12.2 Case Report Forms

In lieu of a CRF set, a System Variable Attribute Report (SVAR) will be used to document all questions and data elements to be collected in the database for this protocol. The NCI/DCP approved SVAR will be used to create the electronic data entry pages in the OnCore database. Amendments to the SVAR will be submitted to the DCP Protocol Information Office for review and approval. Data will be extracted from source documents submitted by the PO.

### 12.3 Source Documents

To standardize the collection of study data, the CLO will provide the PO's with protocol specific Visit Guides and Source Document Worksheets to insure that all required data elements are captured. These documents will be used to supplement data collected on primary clinical source documents. All data reported must be documented either on a separate source document found in the participant's medical record or on the Visit Guides and Source Document Worksheets. All source documents must be signed by the study team member that collected or elicited the information in the source documents. Source documents will be submitted to the CLO (by fax or e-mail) for entry into the OnCore database within 10 business days of each study contact. Primary clinical source documents will be de-identified and relabeled with the participant's PID number prior to submission. Documents containing participant personally identifiable information that has not been completely obscured cannot be accepted and will be returned to the site.

#### **12.4 Data and Safety Monitoring Plan**

All of the procedures outlined in the University of Wisconsin Chemoprevention Consortium standardized Data and Safety Monitoring Plan (approved 03/20/2018). The UW Chemoprevention Consortium Data and Safety Monitoring Committee meets every 6-12 months to review all data from ongoing consortium studies. Members review pooled, unblinded safety data to assess ongoing human subject safety.

#### **12.5 Sponsor or FDA Monitoring**

The NCI, DCP (or their designee), pharmaceutical collaborator (or their designee), or FDA may monitor/audit various aspects of the study. These monitors will be given access to facilities, databases, supplies and records to review and verify data pertinent to the study.

#### **12.6 Record Retention**

Clinical records for all participants, including CRFs, all source documentation (containing evidence to study eligibility, history and physical findings, laboratory data, results of consultations, *etc.*), as well as IRB records and other regulatory documentation will be retained by the Investigator in a secure storage facility in compliance with Health Insurance Portability and Accountability Act (HIPAA), Office of Human Research Protections (OHRP), Food and Drug Administration (FDA) regulations and guidance, and NCI/DCP requirements, unless the standard at the site is more stringent. The records for all studies performed under an IND will be maintained, at a minimum, for two years after the approval of a New Drug Application (NDA). For NCI/DCP, records will be retained for at least three years after the completion of the research. NCI will be notified prior to the planned destruction of any materials. The records should be accessible for inspection and copying by authorized persons of the Food and Drug Administration. If the study is done outside of the United States, applicable regulatory requirements for the specific country participating in the study also apply.

#### **12.7 Cooperative Research and Development Agreement (CRADA)/Clinical Trials Agreement (CTA)**

N/A

### **13. STATISTICAL CONSIDERATIONS**

#### **13.1 Study Design/Description:**

This is a randomized, placebo-controlled, phase IIB oral cavity/oropharynx window of opportunity cancer chemoprevention study of ACTOplus met® XR (pioglitazone 30 mg and metformin extended release

1000 mg) daily for 10-21 days in subjects undergoing planned surgery or definitive radio/chemotherapy. The study population consists of newly diagnosed subjects  $\geq 18$  years of age with biopsy proven, stage I-IV squamous cell carcinoma, or squamous cell carcinoma in situ of the oral cavity or oropharynx who will be undergoing surgical, radiation or combined modality treatment.

The primary endpoint of the study is the absolute change in proliferation index (Ki67) expression in oral cavity cancer cells from baseline to post-exposure. We will evaluate the difference between the treated and control arms in absolute change in Ki67 using two-sample Student's t-test or Wilcoxon rank-sum test, as appropriate.

### 13.2 Randomization/Stratification:

Subjects will be randomized in a 2:1 ratio between ACTOplus met® XR and placebo using permuted blocks of size 3. Each block will have a random permutation of two subjects with ACTOplus met® XR and one with placebo. To facilitate timely dispensing of the study agent, each site will receive a block of 3 bottles of study agent upon receipt of drug shipment authorization. When the site has dispensed their last kit from the block of 3, another block of three bottles will be sent until the site has reached the accrual limit assigned in their sub-award. If a site cannot complete a block in accordance with the accrual goals for the study, the site's sub-award will be amended and their remaining accrual slots will be transferred to another site. To preserve the permutation, the site must continue to make every effort to complete a block once they have received it. Due to the small sample size, there will be no stratification analysis per site.

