#### 5.7.2.2 Pill count:

**Note: Due to a size discrepancy between the placebo and the active study agent, in order to preserve the study blind, pill counts should not be performed by a member of the study team. The count of returned tablets should be performed by the pharmacy or by an independent third party and reported to a member of the study team for documentation in the Visit Guide and compliance calculation.**

Each participant will be provided with a single bottle of study agent containing 25 doses of study agent. Participants will be instructed to bring this study agent bottle and any unused tablets back with them to their end of study visit. The number of returned doses of study agent will be subtracted from the number of doses dispensed to calculate the number of tablets that were taken during the dosing period (Day 1 – end of study dose). This number will be divided by the number of doses of study agent expected to be taken had the participant taken the study agent daily as prescribed. The resulting number x 100 will equal the % compliance.

$$\# \text{ of tablets taken} \div \# \text{ tablets prescribed for the dosing period} = \underline{\quad} \times 100 = \% \text{ compliance}$$

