An NCI, DCP-sponsored nonclinical study evaluated the combination of metformin and pioglitazone for synergistic or additive effects in cancer prevention. In a benzo[*a*]pyrene-induced lung carcinogenesis model, mice were administered metformin (850 mg/kg-bw/day), pioglitazone (15 mg/kg-bw/day), or the combination (same doses) for nine weeks after the last carcinogen dose, with animal sacrifice seven weeks later. Metformin alone caused a 37% reduction ( $p < 0.01$ ) in tumor multiplicity compared with control treatment, whereas pioglitazone alone resulted in a 17% reduction (non-significant) [52]. The metformin plus pioglitazone combination reduced tumor multiplicity by 44% compared with control treatment, suggesting that the two agents work together to reduce tumor multiplicity.

The formulated drug product, ACTOplus met® XR, contains 30 mg pioglitazone and 1000 mg metformin hydrochloride, along with the following inactive excipients: candelilla wax, cellulose acetate, povidone, hydroxypropyl cellulose, lactose monohydrate, magnesium stearate, hypromellose, polyethylene glycols (PEG 400, PEG 8000), sodium lauryl sulfate, titanium dioxide, and triacetin. The tablet consists of an extended-release, osmotically-active core of metformin surrounded by a semipermeable membrane and coated with a pioglitazone drug layer. Two laser-drilled exit ports exist in the membrane, one on either side of the tablet. The semipermeable membrane is permeable to water but not to higher molecular weight components of biological fluids. Upon ingestion, the pioglitazone layer is dissolved; water is then taken up through the membrane, which in turn dissolves the metformin core and excipients, which exit through the laser-drilled ports in the membrane. The rate of drug delivery is constant and dependent upon the maintenance of a constant osmotic gradient across the membrane. The membrane coating remains intact during the transit of the dosage form through the gastrointestinal tract, and is excreted in the feces.

Matching placebo tablets will be manufactured containing lactose monohydrate, microcrystalline cellulose, croscarmellose sodium and magnesium stearate.

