### **6.4 Agent Distribution**

Agents will only be released by NCI, DCP after documentation of IRB approval of the DCP-approved protocol and consent is provided to DCP and the collection of all Essential Documents is complete (see DCP website for description of Essential Documents). These Essential Documents should be submitted to the CLO for processing. When a site has submitted all of the required documents, the DCP's Regulatory Contractor will issue Drug Shipment Authorization for that site. No study agent will be shipped to a site until the Drug Shipment Authorization has been issued and a study initiation visit or teleconference has been completed.

The request for study agent to be shipped to each site will be generated by the CLO using the DCP Clinical Drug Request form (NIH-986). At the time of study initiation, the CLO will request complete shipping contact information for the site's investigational pharmacy. If the site does not have an investigational pharmacy, the complete shipping contact information for the person responsible for study agent accountability at the site will be requested. DCP guidelines require that the agent be shipped directly to the institution or site where the agent will be administered. DCP does not permit the transfer of agents between institutions (unless prior approval from DCP is obtained). The CLO will submit study agent requests to:

[name]  
MRIGlobal  
DCP Repository  
[name]  
[name]  
[contact]  
[contact]  
Emergency [contact]

Participants in this study are randomized on a 2:1 ratio of ACTOplus met® XR:placebo using permuted blocks of 3. Prior to study activation, study statisticians will provide MRIGlobal with a sequential list of 5-digit randomization numbers divided into blocks of 3. Each randomization number will be linked to a treatment assignment - active study agent (ACTOplus met® XR) or placebo. Within each block of 3 randomization numbers, two of the numbers will be assigned to active study agent and one will be assigned to placebo. The CLO will be provided with the list of randomization numbers in blocks of 3 but will not receive the treatment assignment information. Only MRIGlobal and the study statisticians will have access to the treatment assignment information.

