## 6.9 Blinding and Unblinding Methods

To ensure this trial is conducted in a double-blinded manner, the randomization code will be maintained in a password-protected database by the Statistical Center at UWCCC. Unblinding will not occur until all participants have completed the study and study data collection and analysis has been completed.

If a participant experiences a medical issue that requires knowledge of the intervention assignment for appropriate medical management, the assignment may be determined by removing the scratch-off label on the tear-off portion of the study agent bottle label. The following process should be followed:

6.9.1 The treating physician contacts the Protocol Principal Investigator, [name]. with the request to unblind.

[name]., PhD  
Associate Professor of Otolaryngology, University of Minnesota

[name]  
[name]  
[name]  
[contact]  
[contact]  
E-mail address: [[contact]](mailto:[contact])

6.9.2 The request will be approved upon the agreement of the NCI medical monitor for the protocol.

Please note: If the PI or medical monitor is unavailable to provide consent to unblind in a timely fashion, and it is in the participant's best interest not delay unblinding, the blind may be broken without waiting for PI or medical monitor consent. The following steps will still be followed:

6.9.3 The requesting site will notify the CLO ([[contact]](mailto:[contact])) immediately of the unblinding.

6.9.4 The unblinding process will be documented in the participant's study chart.

6.9.5 The participant will be removed from the study.

6.9.6 The CLO will submit formal notification that the blind has been broken to the NCI Medical Monitor.

[name]  
Chief, Lung & Upper Aerodigestive Cancer Research Group  
NCI/Division of Cancer Prevention  
[name]  
[name] (For FedEx, use [name])  
[contact]  
[contact]  
email: [[contact]](mailto:[contact])

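### Fixed blocks of 3, printed in the protocol and shipped to a site one block at a time, let one recognised or unblinded placebo reveal the rest of its block

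*Combined protocol and SAP*

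**What the plan says.** Section 13.2 fixes the block size: "Subjects will be randomized in a 2:1 ratio between ACTOplus met® XR and placebo using permuted blocks of size 3". It also fixes the content of each block: "Each block will have a random permutation of two subjects with ACTOplus met® XR and one with placebo". Section 6.4 repeats the content for the bottle numbers: "two of the numbers will be assigned to active study agent and one will be assigned to placebo". Supply follows the blocks, since "each site will receive a block of 3 bottles of study agent upon receipt of drug shipment authorization". Under Section 6.8.2 the CLO confirms eligibility and then issues the site's next bottle number in order. Section 6.4 describes what the CLO holds: "The CLO will be provided with the list of randomization numbers in blocks of 3 but will not receive the treatment assignment information". No section varies or conceals the block size.

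The two supply passages disagree on timing. Section 6.4 has the next block discussed once two of the three bottles are dispensed. Section 13.2 has it sent after the last one.

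On the blind, Sections 5.7.2.2 and 7.2.12 keep pill counts away from the study team, and give the reason: "Due to a size discrepancy between the placebo and the active study agent". Sections 6.1 and 6.3 nevertheless describe the placebo as matching, and Section 5.2.1 lets either a pharmacist or a study team member dispense. Under Section 6.6 the tear-off label with the concealed assignment is kept centrally during participation and then filed in the participant's study binder. Section 6.9 allows emergency unblinding from that label. It may go ahead without prior consent if the principal investigator or medical monitor cannot be reached in time.

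**The concern.** A block holding two active bottles and one placebo has only three possible orders. Anyone who knows the block limits and learns that one bottle is placebo knows that the other two are active. Anyone who knows the first two knows the third. If the first bottle is learned to be active, the chance of placebo for each of the other two rises from 1/3 to 1/2.

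Two things are at stake. The first is allocation concealment: a site team choosing whom to approach could know what the next bottle contains. Section 3 expects 0.5 to 1 participant per site per month and dosing lasts 10 to 21 days, so the previous participant will often have finished before the next is randomised. The second is the blind of participants still on agent, which an unblinding elsewhere in their block can break indirectly. Adverse event attribution feeds the dose-modification table in Section 5.6, so that loss reaches beyond the endpoint.

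The comparison has little built-in protection. Section 13.4 plans a two-sample t-test or Wilcoxon test on absolute change with no stated covariate, Section 13.2 names no stratification factor, and the placebo arm has 12 evaluable (13 randomised) participants.

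**Working it through.** **Inputs.** Block of 3 with two active (A) and one placebo (P), from Sections 6.4 and 13.2. 39 randomised (26:13), from Section 13.3, which is 39/3 = 13 blocks. The documents give no predictability figure to reproduce.

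**Step 1: every earlier assignment in the block is known.** The three orders are equally likely. An assignment is certain when only one arm is left in the block.

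| Order | Certain assignments | Which |
|---|---|---|
| A A P | 1 | third |
| A P A | 1 | third |
| P A A | 2 | second and third |

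Mean per block = (1 + 1 + 2)/3 = 4/3. Share = (4/3)/3 = 4/9 = 44.4%. By position: first 0%, second 33.3%, third 100%.

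Over 13 blocks the expected number is 13 × 4/3 = 17.3 of 39. Each block contributes 1 or 2, so a realised list can give 13 to 26 (33% to 67%). The count is 13 + Binomial(13, 1/3), with a central 95% range of 14 to 21.

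**Step 2: partial knowledge.** Assume that each earlier assignment is known independently with probability q. The documents give no value of q.

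- Second position is certain if the first was placebo and is known: q/3.
- Third position is certain if the placebo came earlier and is known (2q/3), or if both earlier bottles were active and both are known (q²/3).
- Share = [q/3 + 2q/3 + q²/3]/3 = q/3 + q²/9.

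| Assumed q | Share certain |
|---|---|
| 0.10 | 3.4% |
| 0.25 | 9.0% |
| 0.50 | 19.4% |
| 0.75 | 31.3% |
| 1.00 | 44.4% |

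**Step 3: other block sizes, full knowledge.** A block of 6 (four active, two placebo) has 15 orders. The sixth position is certain in 15 of them, the fifth in 7, the fourth in 3 and the third in 1. Mean = 26/15 = 1.73, and share = 1.73/6 = 28.9%.

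For equal numbers of blocks of 3 and 6 with sizes known, the share is (4/3 + 26/15)/9 = 34.1%. If sizes and boundaries are concealed it is lower, by an amount not calculated here.

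**The case against.** The strongest reply is that 44% presupposes a failed blind. Only the drug repository and the statisticians hold the assignments (Section 6.4), the code is password-protected (Section 6.9), and pill counts are done outside the study team. This stands. The documents do not show that assignments are routinely disclosed, and at q = 0.10 the share is 3.4%. Nor is 44% a ceiling on a single list: it is the expected share under full knowledge.

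A reader might infer further routes to the assignment. The documents do not carry them:

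- **Excreted shell.** Section 6.1 says of the active tablet: "The membrane coating remains intact during the transit of the dosage form through the gastrointestinal tract, and is excreted in the feces". No section says that participants are told of this or report it.
- **Diarrhoea.** The 53.2% versus 11.7% in Section 6.2 is for metformin monotherapy, with no dose or duration given. Even at face value with 2:1 allocation, P(active given diarrhoea) = (2/3 × 0.532)/(2/3 × 0.532 + 1/3 × 0.117) = 90%, and P(placebo given none) = (1/3 × 0.883)/(1/3 × 0.883 + 2/3 × 0.468) = 49%. It makes no assignment certain.
- **Notice to the CLO.** Section 6.9.3 says "The requesting site will notify the CLO" of the unblinding. It does not say that the arm is disclosed.

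On harm, Ki-67 results cannot steer selection before the first batch, because slides are not cut until the 18th participant has completed (Section 10). The monthly recruitment log in Section 4.4 gives a partial audit trail of who was eligible. Both points stand, and no bias in the Ki-67 comparison has been estimated.

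Finally, small blocks serve a stated logistic purpose and hold the 2:1 ratio under site accrual limits. If the tablets reveal the arm, a participant is unblinded whatever the block size. That is true, but it leaves the second harm untouched: a fixed, published block turns one recognised assignment into knowledge of others, including people not yet randomised.

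**Conclusion.** The point holds as a conditional weakness in concealment that is cheap to reduce. The block structure is certain from Sections 6.4, 6.8.2 and 13.2. The size is an expected 44% of assignments (about 17 of 39) if all earlier assignments in a block were known, and less otherwise.

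Two routes rest on the documents' own words and are not closed by the stated safeguards: the tablet-size discrepancy combined with dispensing by study team members, and site-held scratch-off labels with emergency unblinding. Neither is shown to operate routinely. The documents do not say which tablet is larger or that dispensing staff see the tablets, and unblinding is an exception that normally needs agreement from the principal investigator and the medical monitor.

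It would go too far to conclude that 44% of this trial's assignments are in fact predictable, or that the primary result is biased. The sample-size figures are unaffected.

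**What to change.** For blocks not yet shipped, change Sections 6.4 and 13.2 as follows:

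1. Generate each site's list with randomly mixed blocks of 3 and 6, keeping 2:1.
2. Give the CLO and the sites one continuous list of numbers per site, without block boundaries.
3. Resupply by stock level rather than one block per shipment, and reconcile the two resupply rules in Sections 6.4 and 13.2.
4. Move the block size from the site-facing protocol to the statisticians' randomisation file.

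The cost is a regenerated list, a protocol amendment and a few more bottles held on site. The statistical price is balance. A site that stops after four active participants in a block of 6 leaves two planned placebo participants unfilled, against at most one in a block of 3. With 13 planned placebo participants that is worth watching when slots are transferred between sites.

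The change limits deduction within a block. The size discrepancy needs its own remedy, and the descriptions of the placebo as matching should be reconciled with Sections 5.7.2.2 and 7.2.12.
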